Landspatientregisteret (LPR) is a national and clinical database administered by the Danish Health Authority since 1976. All information generated when a patient is treated by the public health service is reported here. In addition to information regarding procedures and admissions, the register contains information on residence, partner status, level of education, income, comorbidities and emigration amongst others. Operations are recorded according to the NOMESCO classification, while diagnoses are coded according to the ICD-10 classification.

Identification of primary procedures

We will determine the cohort of primary procedures from DKR (called P-DKR) by identifying all primary procedures performed from January 1st 1998 to December 31st 2021. P-DKR is then transferred to Danmarks Statistik (DS). Through DS, all primary procedures in the observation period will be identified using NOMESCO operation codes (KNGB*) and these will be collected in a cohort called P-SD. P-DKR and P-SD will be joined into a cohort called PRIM and this cohort will best describe all primary procedures performed in Denmark during the observation period.

Identification of revision procedures

The DKR cohort of revisions (R-DKR) will be identified by all registrations marked as revisions during the observation period. R-DKR is also transferred to DS. All revisions will be identified in DS as R-DS using the NOMESCO operation codes KNG* (knee procedure), KNGC* (revision of knee), KNGG* (arthrodesis) and KNFQ19 (femur amputation). The cohorts R-DKR and R-DS will be combined and called REV. This cohort will best describe revision procedures performed in Denmark during the observation period.

Insertion of cement spacers presents a special registration problem, as different registration practices exist. Some use KNGS codes (eg KNGC59A – Insertion of spacer in a knee joint in connection with revision). We intend to not consider spacer insertion as a revision. For example a two-stage revision will be considered as one revision.

Organization of data

A table (G) with PRIM and REV will be created. G will contain information on revisions, deaths, disappearances, emigration and the associated dates. For each knee joint in PRIM and for each date in the observation period, it will be possible to describe the status of the knee joint.

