In the event of a discrepancy between data from DKR and DS, data from DKR will be chosen, but specific rules will be created for specific situations. In case of missing data for indication for revision (for example if a procedure is not registered in DKR), DS diagnosis codes will be used.

Data is obtained from both registers, as the degree of completeness is very high in both registers. By combining data a near-perfect data collection of the population is ensured.

Description of data from DKR

The Regions' Clinical Quality Development Program (RKKP) manages data from DKR. After receiving approval from PACTIUS, RKKP was queried for data-extraction. Data has since been acquired. Data consists of primary and revision procedures performed from January 1st 1998 to December 31st in 2021. The data includes information regarding:

CPR-number (personal identification number)

Sex

Hospital

Department

Laterality of procedure

Height

Weight

Revision (yes/no)

Indication for procedure

Operation date

Type of arthroplasty

Femur fixation (Cement, yes/no)

Tibia fixation (cement, yes/no)

Femur component

Tibial component

Patella component (yes/no)

Patella fixation (cement, yes/no)

Femur stem (yes/no)

Tibia stem (yes/no)

Operating room

Use of tourniquet (yes/no)

Use of drain

Number of previous revisions

Indication for revision

First revision date

Description of data from LPR

Danmarks Statistik contains many registers about the population in Denmark, including registers regarding place-of-residence, income, education, partner-status, as well as Landspatientregisteret, which contains all information created when a patient is admitted to a public hospital. DS also contains information regarding all treatments performed in privately owned hospitals.

An application has been submitted regarding the acquisition of data from primary and revision arthroplasties performed from January 1st 1998 to December 31st 2021. The requested variables are as follows:

Name

Social Security number

Address

Changes of residence, including information on movements, emigration, disappearance, death

Income

Diagnoses/comorbidities

Operations with operation code: KNGB*, KNGC*, KNGG* and KNFQ19

Level of education

Partner status

Employment status

Statistics

After extraction of data, pooling of data in DS, creation of the populations and tables as described in the previous section on data extraction, statistical analyzes will be carried out.

WPA1

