**Data management, Landspatientregisteret:**

ID-key: unique identification key specifying patient. This key is an anonymized ID key in character format, and hence, is **not** equal to the CPR-number of the participants.

Date of surgery: The date that the procedure took place. In character (date) format.

Code for procedure: NOMESCO procedure codes are used in Landspatientregisteret. KNGB\* codes specify primary procedures, whereas KNGC\* codes specify revision procedures.

Definition of major revisions in Landspatientregisteret

Revision procedures are marked with KNGC\* codes. The following KNGC codes define a major revision:

- KNGC01: Secondary insertion of proximal component of uncemented partial prosthesis in knee
- KNGC02: Secondary insertion of distal component of uncemented partial prosthesis in knee
- KNGC03: Secondary insertion of patellofemoral component of uncemented partial prosthesis in knee
- KNGC04: Secondary insertion of multiple components of uncemented partial prosthesis in knee
- KNGC11: Secondary insertion of proximal component of cemented partial prosthesis in knee
- KNGC12: Secondary insertion of distal component of cemented partial prosthesis in knee
- KNGC13: Secondary insertion of patellofemoral component of cemented partial prosthesis in knee
- KNGC14: Secondary insertion of multiple components of cemented prosthesis in knee
- KNGC19: Secondary insertion of cemented partial prosthesis in knee without specification
- KNGC20: Secondary insertion of all components in uncemented total prosthesis in knee
- KNGC21: Secondary insertion of proximal component in uncemented total prosthesis in knee
- KNGC22: Secondary insertion of distal component in uncemented total prosthesis in knee
- KNGC24: Secondary insertion of multiple components un uncemented total prosthesis in knee
- KNGC29: Secondary insertion of uncemented total prosthesis in knee without specification

KNGC30: Secondary insertion of all components of hybrid total prosthesis in knee  
KNGC31: Secondary insertion of proximal component of hybrid total prosthesis in knee  
KNGC32: Secondary insertion of distal component of hybrid total prosthesis in knee  
KNGC34: Secondary insertion of more than one component of hybrid total prosthesis in knee  
KNGC39: Secondary insertion of hybrid total prosthesis in knee without specification  
KNGC40: Secondary insertion of all components of cemented total prosthesis in knee  

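### The protocol's code filter for revisions includes the wildcard `KNG*`, which also captures the primary codes `KNGB*`, and no written step removes them for WP-A2 and WP-A3

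*Protocol*

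**What the plan says.** **Primaries.** Under Identification of primary procedures, the protocol says that in Danmarks Statistik (DS) "all primary procedures in the observation period will be identified using NOMESCO operation codes (KNGB" and the wildcard that completes that prefix.

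**Revisions.** The next subsection says: "All revisions will be identified in DS as R-DS using the NOMESCO operation codes KNG* (knee procedure", and the list continues with "KNGC* (revision of knee), KNGG* (arthrodesis) and KNFQ19 (femur amputation". The DS revisions are then merged with those from the Danish Knee Arthroplasty Register (DKR): "The cohorts R-DKR and R-DS will be combined and called REV". The same subsection says that spacer insertion will not count as a revision.

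**Data request.** Under Description of data from LPR, the procedures applied for are: "Operations with operation code: KNGB*, KNGC*, KNGG* and KNFQ19". The bare wildcard `KNG*` is not requested.

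**Conflicts between registers.** Under Organization of data: "In the event of a discrepancy between data from DKR and DS, data from DKR will be chosen, but specific rules will be created" for particular situations.

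**SAP.** Section 3, Data management, Landspatientregisteret, separates the two groups: "KNGB\* codes specify primary procedures, whereas KNGC\* codes specify revision procedures". It then itemises the major and minor revision codes, with no `KNG*` wildcard. The SAP's objective is incidence and prevalence only. Section 3 also leaves arthrodesis and amputation out of that study. Section 4 lists no deviations from the protocol.

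**The concern.** A prefix wildcard takes everything beneath it. `KNG*` is the parent of `KNGB*` (primary), `KNGC*` (revision) and `KNGG*` (arthrodesis). Listing it makes the separate `KNGC*` and `KNGG*` entries redundant and brings in the one group that must stay out.

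REV supplies the events for every n-grade quantity. In WP-A2 the risk of an n-grade revision is the number of n-grade revisions divided by the number of knees with n-1 revisions. WP-A3 builds lifetime risk on the WP-A2 results. If a primary counts as an event:

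- an unrevised knee has a grade 1 event on the day it was first operated;
- a true first revision is counted as grade 2, and so on upward;
- the project's threshold for a multiply revised knee, three revisions, is reached after two true ones.

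A fault this large would probably be noticed at analysis. The more realistic harm is a correction made without a record, leaving Studies 2 and 3 with a different event definition from Study 1.

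**Working it through.** The documents give no figure for the size of the DS revision cohort, so there is nothing to reproduce. The check has four parts.

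**1. Prefix match.** Codes or prefixes named in the documents were compared with the protocol's revision filter, the same filter without `KNG*`, and the data request.

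| Code | Matches filter | Matches filter without `KNG*` | In data request |
|---|---|---|---|
| `KNGB09`, `KNGB14`, `KNGB99` | yes | no | yes |
| `KNGC02`, `KNGC59A`, `KNGC99` | yes | yes | yes |
| `KNGG*` | yes | yes | yes |
| `KNFQ19` | yes | yes | yes |
| `KNGS49` | yes | no | no |
| any other `KNG` code | yes | no | no |

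The `KNGB*` codes reach the revision cohort only through the wildcard, and they are in the extract. They therefore fall in both the primary and the revision cohort. Other `KNG` operations match the filter but are not requested, so they cannot enter from the extract described.

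**2. Scale in the worst case.** The inputs are from the protocol's Background: more than 150,000 primaries and more than 20,000 revisions over about 20 years; about 10,500 primaries and 1,048 revisions in 2020. The assumptions are that the filter is run literally, every primary carries a `KNGB*` code in LPR, each operation is counted once in REV, and nothing is reconciled with DKR.

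- 20 years: 150,000 + 20,000 = 170,000 records. Share that are primaries = 150,000 / 170,000 = 88%. Inflation = 170,000 / 20,000 = 8.5 times.
- 2020: 10,500 + 1,048 = 11,548 records. Share = 10,500 / 11,548 = 91%. Inflation = 11,548 / 1,048 = 11.0 times.

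These are rounded background counts over about 20 years, whereas the observation period is 24 years, so they show order of size only.

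**3. Effect on the WP-A2 formula under the same assumptions.** Grade 1 risk = knees with a grade 1 event / knees with no revision = 150,000 / 150,000 = 100%. The true first revisions appear at grade 2. The Background's figure of around 13% revised for the first time within 20 years would then be read as the risk of a second revision.

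**4. After removing the wildcard.** No `KNGB*` code matches, while `KNGC*`, `KNGG*` and `KNFQ19` still do. On the same counts the set returns from 170,000 to 20,000, and for 2020 from 11,548 to 1,048.

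**The case against.** The strongest reply is that this is a drafting slip that the rest of the plan corrects. Much of it is fair.

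- **Intent.** The paragraph just before assigns `KNGB*` to primaries, the wildcard makes its neighbours redundant, and it is absent from the data request. The Background defines a revision as a reoperation, which a first operation cannot be. A slip is therefore likely. But the Background gives a concept without codes, and the text does not show which code was meant.
- **DKR prevails.** DKR carries a yes/no revision field, and a primary marked no in DKR but placed among the DS revisions is a discrepancy. The table that joins primaries and revisions would also make the overlap visible. This would shrink the error, but the specific rules are still to be written, and the general rule cannot reach primaries recorded only in LPR. As an illustration, suppose that DKR's 97% completeness in 2014 held for all primaries throughout. LPR-only primaries would then be 0.03 × 150,000 = 4,500, or 4,500 / (4,500 + 20,000) = 18% of REV. Registration became mandatory only in June 2006, so earlier completeness may differ.
- **WP-A2 inherits from WP-A1.** The Statistics section bases WP-A2 on the population defined in WP-A1, and the SAP implements WP-A1 with a clean split. But what is inherited is the population. No text says that the SAP's event codes replace the protocol's for WP-A2 or WP-A3.

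Three stronger readings are tempting and are not supported. A reader might infer that all non-revision knee surgery would be counted; the data request rules that out. A reader might take 88% as the expected contamination; it is a ceiling under the stated assumptions. A reader might conclude that Study 1's results are affected; they are not, if the SAP is followed.

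**Conclusion.** The point holds in a limited form. As written, the protocol's filter puts every LPR-coded primary into REV as a revision, and no documented step removes it. The exposure lies in WP-A2 and WP-A3, for which this filter is the only code-level event definition in the documents.

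The worst case is 88% of REV over about 20 years. The actual effect depends on how the registers are reconciled, which the protocol leaves open. This should be corrected before Studies 2 and 3 are analysed.

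Deleting the wildcard alone would not bring the three studies into line, because two further code differences remain:

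- The SAP counts `KNGS49` as a minor revision, but the protocol's data request does not include it.
- The protocol does not treat spacer insertion as a revision, with `KNGC59A` as its example code, whereas the SAP lists `KNGC59A` as a minor revision.

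**What to change.** 1. In the protocol, Identification of revision procedures, delete `KNG*` or replace it with the specific revision codes meant. State that `KNGB*` records never enter REV.
2. Hold `KNGG*` and `KNFQ19` as separate end states and not as n-grade revisions. This agrees with WP-A3, which poses arthrodesis and amputation as a risk event in their own right, and with the SAP, which leaves them out of the incidence and prevalence study.
3. Use one itemised revision code list for all three work packages. Reconcile the protocol filter, the LPR data request and the SAP list, including `KNGS49` and the status of `KNGC59A`. The investigators must settle the spacer rule; the point here is that the two documents must agree on it.
4. Record any difference that remains between SAP and protocol in SAP section 4. An entry there does not bind Studies 2 and 3, so carry the same list into their analysis plans.

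The cost is a short protocol edit, a shared code table and, if differences remain, a deviation entry. No new data are needed for the wildcard itself. If `KNGS49` is kept, check that the extract contains it, since the request as described does not.

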Quinn et al. found a lower prosthesis survival of 93.5% for revisions compared to primary knee arthroplasty after 2 years of follow-up, as well as a patient satisfaction of 85% (29). It was found that factors associated with a good patient reported postoperative outcome following revision were male sex and fewer previous revisions on the same knee (29). Verbeek et al. described a satisfaction rate of 53% after 5 years following revision (30). However, most patients report a satisfactory outcome after revision and that most patients improve postoperatively, as a meta-analysis by Saleh et al. showed (40-42).

The indication for revision has also been found to be important for the result after revision. Abram et al. and Yao et al. found in register studies, that for revision due to infection or fracture the mortality was significantly higher than for non-acute reasons for revision (43, 44).

In rare cases, some patients may end up with either an arthrodesis or amputation. These complications have been investigated in the Danish population by Gottfriedsen et al. In the

period 1997 to 2013, the cumulative incidence of primary knee arthroplasties that ended with an arthrodesis was found to be 0.26% (6). For transfemoral amputations, the cumulative incidence in the same period and for the same patient population was found to be 0.32% (7).

No studies examining functional outcomes after re-revision surgery were found. A Danish study by Lindberg-Larsen et al. studied a cohort of revision patients. It was found that Length-of-stay (LOS) >5 days were associated with previous revision. Reasons for prolonged LOS were pain, lack of mobilization and anaemia (40).

Klasan et al. found a lower risk of re-revision when all prosthetic parts were replaced, compared to exchange of only the femoral or tibial prosthesis (11). It was also found that patients with low ASA scores and longer time between primary TKAs had better OKS scores 6 months after revision.

Costs

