- 1) What is the annual incidence of revisions of various degrees, and how has the incidence changed during the last 20 years?
- 2) What is the current prevalence of n-grade revisions, and how has the prevalence changed during the last 20 years?
- 3) What is the relationship between the annual incidence of revisions of n-grade with the incidence of primary procedures in the preceding years?

WP-A2: Cumulative Revision Rates (CRR)

The purpose of this WP is to determine the cumulative revision rate (CRR) for revisions of different grades (number of previous revisions) to generate information that can be used for informing patients preoperatively.

Research questions:

1. What is the CRR for n-grade revision?
2. Is CRR influenced by demographic and surgical variables such as sex, age, education, implant type, place of residence, income, operative technical conditions and the indication of revision such as infection, aseptic loosening, instability, pain without reason?

WP-A3: Lifetime risk of multiple revisions

The purpose of this WP is to determine the lifetime risk of revision of various grades as well as the lifetime risk of arthrodesis and amputation. These risks will be investigated in relation to demographic and surgical variables.

Research questions:

1. What is the lifetime risk that a patient with a given combination of demographic and surgical variables will need n-number of revisions after primary arthroplasty?
2. As above but with arthrodesis and amputation as the risk event.

Review of literature

To gather relevant background information for this protocol, MEDLINE via pubmed was searched to find relevant literature in the field. The MESH words "knee replacement" and "reoperation" were used. We wanted to identify articles that either described epidemiological findings regarding multiple revision knee arthroplasties or described risk factors associated with repeated revisions. There were no MESH words containing "rerevision", "multiply revisions" or "repeated revisions".

Articles found: 4350 results.

Based on the title, this number of abstracts were reviewed: 97

Of the abstracts, so many articles were reviewed and read: 65

Number of articles used in the protocol: 47.

Material and methods

Design

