In WP-A1 we want to calculate:

- 1) Annual incidence of revision arthroplasties.

Incidence is calculated as the number of n-grade revisions performed in Denmark during a given year as a proportion of the current year's population. This is done for each level of revision.

The incidence rate is also calculated:

$$IR = \frac{\text{Number of } n\text{-grade revisions}}{\text{Number of person-years in observation period}}$$

- 2) The continuous prevalence of revision knees.

Prevalence is calculated as the number of patients living with n-grade revision knee as a proportion of the current year's population. This is done for each level of revision.

- 3) The relationship between the annual incidence of n-grade revisions with the incidence of primary procedures in the preceding years.

$$\text{rate ratio} = \frac{\text{IR for } n - \text{ grade revision}}{\text{IR for primary procedures the previous year}}$$

WPA2

The analyzes will be based on the population defined in WP-A1. We will estimate the cumulative incidence (risk) for the different levels of revision and examine whether factors such as patient demographics, implant type and other operative technical conditions influence the cumulative incidence.

$$\begin{aligned} & \text{risk for } n - \text{ grade revision} \\ & = \frac{\text{number of } n - \text{ grade revisions in the observation period}}{\text{numbers with } n - 1 \text{ revisions}} \end{aligned}$$

To investigate whether patient demographics, implant type, indication for revision and other operative technical conditions have an effect on the subsequent incidence of revision, we will use regression analysis. It will be relevant to investigate possible confounding of the variables.

In addition, we will create "cumulative incidence plots" for each level of revision to illustrate prosthesis survival.

WPA3

The lifetime risk will be determined as a summation of the expected remaining life based on the CRR for the individual events (primary procedure and n-grade revision). As in WPA2, we will examine whether patient demographics, implant type and other operative technical conditions have an effect on the risk of revision. In addition, the lifetime risk of arthrodesis or amputation as an event will also be calculated. Thus, data from WP-A2 becomes the starting point for the calculations.

Applicant's duties

The applicant's duties consist of:

The overall responsibility for the execution of the project.

Obtaining necessary data approvals.

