#### **Data management, for both registers.**

Definition of a revision: A revision is defined as the exchange, addition, or removal of a knee prosthesis component (1). However, knee arthrodesis and amputation are not included in this study.

Definition of major revision: A major revision is defined as exchange of the femoral component and/or the tibial component with subgroups of tibial, femoral and all component exchange (2).

Definition of minor revision: A minor revision is defined as the exchange of polyethylene liner and/or addition or revision of the patella component. Insertion/removal/exchange of spacers are also included in this category (2).

Population: The population is defined as the number of alive citizens in the state of Denmark. Annual populations are defined as the population in Denmark on the 1st of January that year. Additional data for sex and age of the population is acquired. Data for the population is acquired from Danmarks Statistik (3).

In case of disagreement between registers: In cases of discrepancy between the two registers, Landspatientregisteret will overrule the Danish Knee arthroplasty register concerning following variables:

- Laterality
- Date of surgery
- Gender
- Age
- Performing institution

In cases of discrepancy between the two registers, the Danish Knee arthroplasty register will overrule Landspatientregisteret concerning following variables:

- Procedure code
- Revision of tibia
- Revision of femur
- Indication

Calculation of standardized prevalence: Annual standardized prevalence is calculated as the number of patients living with a n-grade revision during a given year as a proportion of the population in Denmark (the 1st of January that year) (3). The prevalence is then multiplied by 100,000 for standardization. This is done for each level of revision, each year. E.g., the standardized prevalence for 1998 is calculated as:

$$\text{Standardized prevalence, 1998} = \frac{\text{Number of knees living in 1998 with a } n - \text{ grade revision}}{\text{Total population in Denmark in 1998}} * 100,000$$

The prevalence is only calculated for revisions performed between January 1st 1998 and December 31st 2021.

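### The protocol places arthrodesis and femur amputation among revisions without saying whether they add a grade or end risk, so grade-specific risks in WP-A2 and WP-A3 are not clearly defined

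*Protocol*

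**What the plan says.** **Event definition.** Protocol, Identification of revision procedures: "All revisions will be identified in DS as R-DS using the NOMESCO operation codes KNG* (knee procedure), KNGC* (revision of knee), KNGG* (arthrodesis"). The list ends with "KNGG* (arthrodesis) and KNFQ19 (femur amputation). The cohorts R-DKR and R-DS will be combined and called REV", which pools these registrations with the arthroplasty register's own revisions. Of REV the protocol says "This cohort will best describe revision procedures performed in Denmark during the observation period". The only exclusion stated there is for spacer insertion.

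**Knee status.** Protocol, Organization of data: "G will contain information on revisions, deaths, disappearances, emigration and the associated dates". The section says the state of each knee can be described at every date. It names no end state for a fused or amputated knee.

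**WP-A2.** Protocol, Statistics: "We will estimate the cumulative incidence (risk) for the different levels of revision". The formula divides the number of n-grade revisions by the number who have had n−1 revisions. The analysis is to use the WP-A1 population.

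**WP-A3.** The first research question concerns the lifetime risk of n revisions. The second reads "As above but with arthrodesis and amputation as the risk event".

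**SAP.** Section 3, under the definition of a revision for both registers: "However, knee arthrodesis and amputation are not included in this study". Section 4 lists no deviations from the protocol. This SAP covers incidence and prevalence only; none is supplied for WP-A2 or WP-A3.

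**The concern.** The documents treat the same two operations in three ways: as members of the revision cohort, as an event distinct from revision, and as excluded. The protocol's Background definition of a revision (a component inserted, removed or replaced) mentions neither operation and does not settle the matter.

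On the protocol's wording, a knee amputated after two revisions becomes a third-revision knee. It then enters the denominator for a fourth revision, which it cannot undergo. Likewise, a knee amputated after three revisions enters the fourth-revision numerator. Both parts of the ratio therefore depend on a rule that is not written.

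The grade-specific cumulative revision rate is intended for informing patients before surgery, and WP-A3 builds lifetime risk on it. The effect would matter most at high grades, where genuine revisions are few and which are the subject of the project.

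**Working it through.** The documents contain no grade-specific count to reproduce, and the SAP states that no sample size was calculated. What follows is a scale check.

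**Inputs from the protocol**
- Primaries: more than 150,000 in 20 years (Background). 150,000 is used.
- Revisions: more than 20,000 in 20 years (Size of the problem). 20,000 is used.
- First revision: 13% at 20 years (Size of the problem).
- Each later grade: 20%, from the English register study cited under Re-revision, at 13, 5 and 3 years.
- Arthrodesis: "the cumulative incidence of primary knee arthroplasties that ended with an arthrodesis was found to be 0.26% (6"). Transfemoral amputation: 0.32%. Both cover 1997 to 2013 (Outcome after revision and re-revision).

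**Assumptions.** The documents give neither the overlap between the two operations nor their spread over grades. Both are shown as ranges.

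**Step 1: number of knees**
- Arthrodesis: 0.0026 × 150,000 = 390
- Amputation: 0.0032 × 150,000 = 480
- Together: 480 knees with full overlap, 390 + 480 = 870 with none
- Against 20,000 revisions: 480/20,000 = 2.4%; 870/20,000 = 4.4%

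**Step 2: illustrative genuine revisions, R**
- R1 = 150,000 × 0.13 = 19,500
- R2 = 19,500 × 0.20 = 3,900
- R3 = 3,900 × 0.20 = 780
- R4 = 780 × 0.20 = 156
- Grades 3 and 4 together: 936

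**Step 3: the WP-A2 ratio**

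Let S_n be the salvage operations counted as an n-th revision.
- As written: (R_n + S_n) / (R_(n−1) + S_(n−1))
- With salvage out of the grade count: R_n / R_(n−1), which is 20% at grades 2 to 4 by construction

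Example, 870 spread equally over grades 1 to 4 (217.5 each):
- Grade 3: (780 + 217.5)/(3,900 + 217.5) = 997.5/4,117.5 = 24.2%
- Grade 4: (156 + 217.5)/(780 + 217.5) = 373.5/997.5 = 37.4%
- Grade 3 and 4 events: 936 + 435 = 1,371, or +46%

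| Assumed spread of 870 over grades 1–4 | Grade 3 risk | Grade 4 risk | Grade 3–4 events |
|---|---|---|---|
| In proportion to revisions | 20.0% | 20.0% | 969 (+4%) |
| All at grade 2 | 16.4% | 20.0% | 936 (0%) |
| 50/30/15/5% | 21.9% | 21.9% | 1,110 (+19%) |
| Equal | 24.2% | 37.4% | 1,371 (+46%) |
| 10/20/30/40% | 25.6% | 48.4% | 1,545 (+65%) |

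With 480 instead of 870 and the same spreads, grade 3 risk runs from 17.8% to 23.1%, grade 4 risk from 20.0% to 37.7%, and grade 3–4 events rise by 0% to 36%.

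**Step 4: direction**

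Where S_(n−1) is not zero, the ratio as written lies between R_n/R_(n−1) and S_n/S_(n−1). It falls below the true value only when S_n/S_(n−1) is the smaller. With 870, grade 3 risk falls in one of the five spreads, is unchanged in one and rises in three. Grade 4 risk is unchanged in two and rises in three.

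**The case against.** The best defence is that the code list is a retrieval filter and not a grading rule. It contains the whole KNG family, which would also capture the KNGB codes used for primaries, so it cannot be meant literally as a count of revisions. Spacer codes fall within the list too, yet the protocol says spacers will not count. WP-A3 separates arthrodesis and amputation from revision grades. The SAP excludes both, and WP-A2 is to use the WP-A1 population. If the SAP definition carries forward, the crude WP-A2 ratio is already R_n/R_(n−1).

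Much of this is fair as a guess at intent, and no sentence says outright that these operations add a grade. But the protocol does say that all revisions will be identified with these codes, and it exempts spacers while leaving these two operations in. Nothing says that the SAP definition governs WP-A2 or WP-A3. Even with that exclusion, the cumulative incidence plots and the regression still need a rule for follow-up after fusion or amputation, and none is given.

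Two stronger readings are tempting. A reader might infer that the next grade's risk is always diluted. That adds salvage to the denominator alone: under the 10/20/30/40% spread, 156/1,041 = 15.0% at grade 4. The same rule also adds salvage to the numerator and gives 504/1,041 = 48.4%. A reader might also infer that WP-A3 counts the operation twice. It would contribute to two separately reported risks, which is not double counting within either.

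**Conclusion.** The point holds as an unresolved definition with material consequences at high grades. The protocol's wording gives a fused or amputated knee an extra grade and states no exit from risk. WP-A3's separate endpoint and the SAP's exclusion point the other way, and no deviation is logged. That such knees stay at risk is inferred from the absence of an exit rule; it is not stated.

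If these operations are counted, the grade reached is overstated by one for each affected knee. The direction of the error in grade-specific risk is not known. The ranges (grade 3 about 16% to 26%, grade 4 from 20% to 48%, grade 3–4 events +0% to +65%) depend on the assumed spread and on 870 knees with no overlap. The 0.26% and 0.32% cover a shorter period than 1998 to 2021, and the reason for amputation is not given. The 20% chain joins different follow-up times from another country's register. The figures show that the choice can matter; they do not estimate the bias. Across all revisions the effect is small, about 2% to 4% in number.

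**What to change.** - **Grade count.** Take KNGG and KNFQ19 out of the revision-grade count. Keep them in table G, with dates, as a separate terminal state.
- **WP-A2.** Treat the first arthrodesis or amputation as a competing event, alongside death, in each grade's cumulative incidence. The knee then enters no later risk set.
- **WP-A3.** Use the operation as the separate endpoint, and as a competing event for further revision.
- **Consistency.** Align the protocol's Identification of revision procedures with the definition in SAP section 3, record the difference in SAP section 4, and state that the same definition applies to all three work packages.

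The cost is small: some wording and one status variable. Both code groups are already in the requested data (Protocol, Description of data from LPR). The downside is slightly fewer high-grade events.
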